6.3 Power for Secondary Outcomes

Comparisons of in-person ESTEEM to waitlist have produced effect sizes of $d = .55$ for depression.²⁹ Average meta-analytic effects for depression ($d = .66$) of iCBT compared to weak control conditions also suggest that randomizing 120 participants provides a $\geq 80\%$ chance of detecting a significant difference ($p < .05$) between the conditions.³¹⁻³⁴ Given the number of secondary outcomes and to guard against Type 1 error, we will focus our results interpretation primarily on effect sizes rather than statistical significance.

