3. STUDY DESIGN

The design is a two-arm, parallel-assignment randomized controlled trial design to test the efficacy of iCBT ESTEEM compared to self-monitoring control. The unit of randomization is the individual. The primary outcome is number of past-30-day CAS with primary or casual partners at 8-mo follow-up, assessed via Timeline Follow-Back. A total of 120 YMSM participants were enrolled in the study ($n = 60$ per condition).

STATISTICAL ANALYSIS PLAN

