5. RANDOMIZATION

5.1 Method of Randomization

Randomization occurred on the participant level. Participants were randomly assigned to receive one of two conditions: iCBT ESTEEM or self-monitoring (N = 120). We used a 1:1 randomization scheme such that for every one participant randomized to iCBT ESTEEM, one participant was randomized to self-monitoring. Participant randomization was stratified based on mental health (i.e., eligible based on depressive symptoms, anxiety symptoms, or both based on the Brief Symptom Inventory-4). Stratified randomization occurred using a random number table generated by SPSS such that 60 participants were randomized to each condition.

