8.4.1 Analysis of Secondary Outcomes: HIV Risk Behavioral and Social-Cognitive Outcomes

Secondary HIV risk behavioral and social-cognitive outcomes at the immediate post-intervention timepoint (4-month follow-up) are: past-30-day condomless anal sex with main or casual partners, past-30 condomless anal sex with casual partners only, safer sex self-efficacy (SSQ), decisional balance for condom use (DBCUS), and past 4-month HIV/STI testing. Secondary outcomes at 8-month follow-up include: 30-day condomless anal sex with main or casual partners, past 30-day condomless anal sex with casual partners only, safer sex self-efficacy (SSQ), decisional balance for condom use (DBCUS), past 4-month HIV/STI testing history, HIV testing results, and syphilis testing results.

Analysis	In these models, we will assess whether ESTEEM iCBT will yield greater reduction in HIV risk behavioral and social-cognitive secondary outcomes at the immediate post-intervention (4-month follow-up) timepoint and the 8-month follow-up. HIV secondary outcomes include: past 30-day condomless anal sex with main or casual partners (TLFB), past 30-day condomless anal sex with casual partners only (TLFB), decisional balance for condom use (DBCUS), past 4-month HIV/STI testing, HIV testing results, and syphilis testing results.
Analysis population	All participants
Endpoint	Immediate post-intervention and 8-month follow-up
Unit of analysis	Participant
Method of analysis	Depending on the outcome we will use repeated measures generalized linear mixed models (for continuous outcomes) and generalized linear mixed models with a logit link (for binary outcomes). We will use maximum likelihood estimation with contrasts to test condition x time comparisons at each relevant timepoint. We will test the best-fitting correlation structure, but based on our previous studies, expect it to be compound

STATISTICAL ANALYSIS PLAN

	symmetrical. In the event of high skew or zero inflation, the appropriateness of modeling a negative binomial or Poisson distribution will be considered.
Handling of missing data	MAR assumption
Adjustment covariates	Adjustment for baseline covariates not balanced at randomization
Type I error	5% (2-sided)
Control of type I error	To control for the false discovery rate, we will apply a Bonferroni correction for each set of moderators (e.g., mental health, minority stress). Primary interpretation will focus on effect sizes.
Treatment effect estimate	Odds ratio with 95% confidence limits

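### SAP 6.3 presents reading secondary results mainly by effect size as protection against Type 1 error, but that reading has no cut-off and no error rate, so it gives no such protection

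*SAP*

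**What the plan says.** SAP 6.3 first makes a power statement for depression. It cites "Average meta-analytic effects for depression ($d = .66$) of iCBT compared to weak control conditions" and says that randomizing 120 gives at least an 80% "chance of detecting a significant difference ($p < .05$) between the conditions". It then turns to the number of secondary outcomes and says that, "to guard against Type 1 error, we will focus our results interpretation primarily on effect sizes rather than statistical significance".

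The same idea appears as a means of error control in the analysis tables. In SAP 8.4.1 the *Control of type I error* row ends "Primary interpretation will focus on effect sizes", and the same sentence is in that row of 8.4.2.1 and 8.4.3.1. SAP 8.6 sends the exploratory outcomes through the 8.4.2.1 approach.

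The same tables keep a two-sided 5% level and 95% confidence limits. They also carry a Bonferroni line, worded for sets of moderators and described as controlling the false discovery rate. The named effect measure is an odds ratio throughout, including for continuous scales. No standardized effect size is defined and no threshold is set.

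**The concern.** A Type 1 error rate belongs to a decision rule that is calibrated to sampling error. Giving the size of the estimate priority over its test removes that calibration. Reading by effect size can be sound description, but it is not error control, and the SAP says that it is.

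The conclusions at stake are those on depression, anxiety, substance use, minority stress, self-efficacy and the moderators. At this sample size, small standardized differences arise often by chance. An ineffective intervention could therefore yield a list of small effects that the SAP would describe as protected. Because no threshold is set, what counts as an effect can also be decided after the results are seen. The primary outcome is not affected.

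**Working it through.** **Inputs.** 60 per arm, 1:1 (SAP 3 and 5.1). 20% attrition (SAP 6.2), leaving 60 × 0.8 = 48 per arm. Two-sided 5% (SAP 8.4.2.1). Depression effects d = 0.66 and 0.55 (SAP 6.3). My assumptions, because the SAP gives no figures: a standardized difference d as the effect size, cut-offs of 0.2 to 0.5, and a baseline–follow-up correlation r of 0.5 where adjustment is shown.

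**The plan's own figure.** Power = Φ(d/√(2/n) − 1.96).
- d = 0.66: at n = 60, Φ(3.615 − 1.96) = 95%; at n = 48, Φ(3.233 − 1.96) = 90%.
- d = 0.55: 85% at n = 60 and 77% at n = 48.

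The statement of at least 80% for 120 randomized therefore reproduces at d = 0.66. It is not in dispute here.

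**Null behaviour of an effect-size reading.** With no true effect, the observed d has standard error √(2/n): 0.204 at 48 and 0.183 at 60 per arm. Baseline adjustment multiplies this by √(1 − r²) = √0.75, giving 0.177 and 0.158. The chance that |d| reaches cut-off c is 2·P(T > c/SE), with 2n − 2 degrees of freedom for the unadjusted case and the normal approximation for the adjusted case. For example, 0.2/0.204 = 0.98 gives 33.0%.

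| Assumed cut-off | 48/arm, unadjusted | 60/arm, unadjusted | 48/arm, r = 0.5 | 60/arm, r = 0.5 |
|---|---|---|---|---|
| 0.2 | 33.0% | 27.6% | 25.8% | 20.6% |
| 0.3 | 14.5% | 10.3% | 9.0% | 5.8% |
| 0.4 | 5.3% | 3.0% | 2.4% | 1.1% |
| 0.5 | 1.6% | 0.7% | 0.5% | 0.2% |

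A simulation of 100,000 null trials per sample size agrees with the unadjusted columns (33.0% and 27.4% at 0.2). Counting only differences in favour of iCBT halves each figure.

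**Where the comparison turns.** A two-sided 5% test corresponds to |d| = 0.405 (48 per arm) or 0.362 (60 per arm) unadjusted. With r = 0.5 it corresponds to 1.96 × 0.177 = 0.35 or 1.96 × 0.158 = 0.31. Cut-offs below these values are looser than the test, and cut-offs above them are stricter.

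**Across the outcomes.** The Study Summary lists 16 secondary outcomes at 4 months and 17 at 8 months, 33 in all. Leaving out the HIV and syphilis kit results gives 31. Expected chance flags at a cut-off of 0.2 are 31 × 0.206 = 6.4 to 31 × 0.330 = 10.2, against 31 × 0.05 = 1.6 for uncorrected 5% tests. Expected counts do not require independent outcomes. At a cut-off of 0.4 with 48 per arm unadjusted, the count is 31 × 0.053 = 1.6, the same as uncorrected testing.

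**The case against.** The SAP sets no threshold, so any flag rate is the reviewer's construction. The standardized effects that the SAP itself cites are 0.40, 0.55, 0.59 and 0.66. Against benchmarks of that size, an effect-size reading is about as strict as a 5% test or stricter. Even at 0.3, with 60 per arm and r = 0.5, the rate is about 6%. The SAP also says primarily, not only, and keeps the 5% level and 95% limits in every secondary table. In a trial of preliminary efficacy, descriptive secondary results are legitimate.

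Most of this stands, and it rules out two stronger readings that a reader might infer. One is that the plan's approach flags null outcomes far more often than a 5% test, whatever the cut-off. That depends on a cut-off the documents do not give, and it reverses above the values shown. The other is that the plan ignores sampling error altogether, which the retained tests and intervals contradict.

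It does not rescue the sentence in 6.3. The cited effects are planning values, and nothing makes them thresholds for interpretation. No sentence requires an interval to exclude no effect. The SAP's stated worry is the number of outcomes, and a cut-off near 0.4 would at best match uncorrected testing in the least precise case. The Bonferroni line is worded for moderators and does not clearly cover the secondary outcomes.

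**Conclusion.** The point holds in a limited form: the SAP claims a protection that its method does not have. Interpretation led by effect size, with no cut-off and no error rate, does not control Type 1 error.

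How much this matters depends on what is later called an effect. At 0.2, a null contrast is flagged about 21% to 33% of the time across the cases shown, and the excess over a 5% test disappears at about 0.31 to 0.41. Stronger correlation with baseline lowers the rates: at r = 0.7, the 0.2 cut-off gives about 17% (48 per arm) and 13% (60 per arm), still above 5%.

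The figures treat every contrast as continuous, although condomless-sex counts and HIV/STI testing history are among the 31. They cover two-group main effects only. Nothing was calculated for the moderator interactions in 8.4.3.1, so for those the point rests on the wording alone.

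**What to change.** In SAP 6.3, delete the statement that reading by effect size protects against Type 1 error. In the *Control of type I error* rows of 8.4.1, 8.4.2.1 and 8.4.3.1, delete the closing sentence on effect sizes. Replace both with the following, and apply it to 8.6:

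> Each secondary, moderator and exploratory effect estimate is reported and interpreted with its 95% confidence interval. A result whose interval includes no effect is described as inconclusive, whatever the size of the point estimate. Except where a named multiplicity procedure is applied to a stated family of tests, these results are not adjusted for multiplicity and are descriptive.

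The interval requirement brings the per-contrast rate back to about 5%. It does not control error across 31 contrasts, which is why the last sentence is needed. If the team wants confirmatory secondary claims, it must name the family and the procedure, because the SAP does not clearly define either for the secondary outcomes.

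The cost is wording only, since 95% limits are already planned outputs. The downside is that fewer secondary outcomes can be described as showing an effect.

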6.4 Power for Exploratory Outcomes

Power analyses were not conducted to inform exploratory outcomes.

7 INTERIM MONITORING

7.1 Overview

Interim monitoring focused on participant accrual, protocol adherence, loss to follow-up, data completeness and quality, safety, efficacy, and futility.

7.2 Safety

The principal investigators were responsible for monitoring the data and assuring protocol compliance. Unanticipated problems involving risks to subjects or others, including adverse events, were followed by a written report within five calendar days of the principal investigator becoming aware of the event to the institutional review board (IRB). Biannual DSMB meetings were held to review the research protocol and planning for data safety and monitoring and evaluate the progress of the trial, including periodic assessments of data quality and timeliness, participant session attendance and assessment completion, participant risk versus benefit, and other factors that may affect study outcomes. The principal investigators apprised the Data Safety Monitoring Board (DSMB) of all unanticipated problems and adverse events that occurred during the conduct of this research project. The DSMB was also informed of serious or unanticipated adverse events.

8 ANALYTIC PLAN

8.1 Overview

The analysis of the primary and secondary outcomes will be according to the principle of intent-to-treat, i.e., participants will be analyzed according to their original treatment assignment regardless of adherence to protocol. All analyses will include the participant as the unit of analysis. SAS 9.4, SPSS 26.0, MPlus 8.4, and the latest version of R (currently 4.0.2) software will be used for all analyses.

STATISTICAL ANALYSIS PLAN

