To assess intervention efficacy, participants will be assessed at three time-points: baseline, immediately post-treatment (4-month follow-up), and 8-month follow-up. Participants will complete validated measures online of past-30-day HIV-risk behavior (e.g., condomless anal sex), mental health (e.g., depression, anxiety), and minority stressors (e.g., discrimination) at all three time points. At 8-month follow-up, participants will be mailed and asked to complete the same at-home HIV/STI testing kit for HIV and syphilis described above.

After completing the baseline assessment, participants randomized to ESTEEM iCBT will be assigned a study therapist and will be contacted by their therapist to schedule a 30-minute introductory call via WeChat (i.e., a Chinese multi-purpose messaging, social media, and payment app; comparable to US apps, such as Google Voice, which the Yale research team has utilized in other studies). During this conversation, therapists will explain the structure of the study and briefly discuss the participant's motivations and goals for participating in the study. Participants will then complete one session per week. If participants miss a session, as determined by daily therapist and RA review of session access and self-monitoring or homework completion, they will receive a reminder to complete the session. Participants will also be asked to schedule a check-in phone call with their study therapist two-weeks post-randomization to discuss their progress through the study sessions. Participants will have a window period of four months (approximately 17 weeks) to complete all 10 sessions.

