Internet-based CBT (iCBT) can overcome barriers to broad implementation of evidence-based HIV-prevention interventions. iCBT, pioneered in Northern Europe to disseminate CBT broadly, involves participants engaging in several CBT tasks hosted on an online platform: reading self-guided psychoeducation, reviewing video demonstrations of more complex skills, completing CBT worksheets, and uploading between-session homework.⁹⁰⁻⁹² Counselors respond to participants' progress (e.g., motivational feedback on worksheets, suggesting homework tasks) within 1-2 days. Participants can also email counselors to clarify points of confusion. Because counselor and participant do not meet "live" at the same time, iCBT is asynchronous in that it allows participants to complete each module anytime anywhere and counselors to then spend an average of only 10 minutes reviewing each module within 1-2 days. Given its efficiency, iCBT counselor caseloads can

reach 200-300. Meta-analyses of iCBT find effects similar to those obtained in face-to-face CBT.^{93,94} In a cultural context of normative concealment and conversion therapy, our highly secure identity-affirmative iCBT offers an urgently needed alternative for tailored, sensitive mental and sexual health support. Indeed, Chinese YMSM expressed strong preferences to receive online versus in-person supports.^{95,96}

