5.2 Number of Participants

A total of 120 YMSM participants will be enrolled in Aim 2 of study ($n = 60$ per condition). Assigning 60 participants to each condition (iCBT vs. self-monitoring) and accounting for 20% attrition, a liberal estimate based on our previous online RCTs (i.e., 93-100%), will provide $\geq 80\%$ chance of detecting a difference ($p < .05$) between the conditions of $d = .40$, which is significantly lower than what we found when comparing in-person ESTEEM to waitlist ($d = .59$ for CAS, $d = .55$ for depression) and lower than even the smallest average meta-analytic effect ($d = .66$) of iCBT compared to weak control conditions for depression. For Aim 3, a total of 55 participants, including ($n = 20$) Aim 2 participants, ($n = 6$) study therapists and supervisors, ($n = 8$) government administrators and leadership, ($n = 7$) LGBTQ community organization staff, and ($n = 7$) medical providers will be interviewed in order to identify themes in regard to barriers and facilitators of implementing iCBT ESTEEM among Chinese YMSM.

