For participants assigned to ESTEEM iCBT, they will be assigned a study therapist and will be contacted by their therapist to schedule a 30-minute introductory call via WeChat. During this conversation, therapists will explain the structure of the study and briefly discuss the participant's motivations and goals for participating in the study. All participants will then complete one session (i.e., ESTEEM iCBT or self-monitoring) per week. If participants miss

a session, as determined by daily therapist and RA review of session access and self-monitoring or homework completion, they will receive a reminder via a WeChat message to complete the session. Participants will also be asked to schedule a check-in WeChat call with their study therapist two-weeks post-randomization to discuss their progress through the study sessions. Participants will have a window period of four months (i.e., 17 weeks) to complete all 10 sessions.

Lastly, all participants will be sent messages on WeChat to complete 4-month and 8-month follow-up assessments. For all assessment time points, automatically generated alerts from Sojump will be sent to CSU study staff in response to any participants who indicate suicidality in response to suicidality assessments, at which point a clinical staff member part of the CSU team will implement the clinical protocol. For the 8-month follow-up, a second at-home HIV/STI testing kit will be mailed to participants. The same procedure as described above will be followed in regard to participants administering this test and reporting results to CSU study counselors for follow-up.

See Table 1 in Section 11.1 for a Visit Schedule Table with study procedures listing all points of data collection.

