Intervention	
1) ESTEEM iCBT: This online CBT treatment consists of 10 weekly modules that participants will complete over the course of 4 months. Modules contain weekly psychoeducational text and vignettes about minority stress and mental health; brief videos illustrating the CBT skills; and homework exercises that therapists review and provide feedback on. Homework exercises include weekly tracking of stress and mood, practicing new skills (e.g., mindfulness, cognitive restructuring), and exercises related to considering the origins of stress and negative emotions that participants may be experiencing. Therapists provide feedback after each homework assignment, including reviewing each participant's treatment goals as part of the first session's homework. Therapists who support this condition will be instructed to incorporate LGBTQ-specific content and feedback into homework reviews. This intervention was culturally adapted for Chinese YMSM and found to be acceptable and feasible.
 
2) Self-monitoring control: In this control condition, participants will be asked to indicate their past 7-day mood, stress experiences, and mental and behavioral health on an online survey. Participants will record these experiences once per week for 10 weeks.

Duration of Intervention	10 weekly modules in up to 17 weeks (four months)
Primary Outcome	Number of past-30-day condomless anal sex (CAS) acts with primary or casual partners as measured by the Timeline Follow-Back at the 8-month follow-up assessment.
Primary Analysis	We will examine the efficacy of the intervention using a generalized linear mixed model to test whether receipt of ESTEEM iCBT vs the self-monitoring control affects changes in the number of past-30 day CAS with primary or casual partners from baseline to 8-month follow up.

STATISTICAL ANALYSIS PLAN

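### iCBT participants share therapists and controls are not assigned one, but no SAP model allows for it; if outcomes correlate within therapist, the arm contrast is overstated in precision

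*SAP*

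**What the plan says.** - **Allocation.** SAP 5.1: "Randomization occurred on the participant level". This is an individually randomised trial, not a cluster trial.
- **Therapists in the iCBT arm.** Protocol 6.1: "For participants assigned to ESTEEM iCBT, they will be assigned a study therapist". That therapist holds a 30-minute introductory call. The SAP Study Summary (Intervention) describes "homework exercises that therapists review and provide feedback on" and adds: "Therapists provide feedback after each homework assignment". There are 10 modules.
- **Control arm.** Participants complete a weekly online survey. Neither document assigns them a therapist. One sentence in Protocol 6.1, on a check-in call with the study therapist two weeks after randomisation, follows a sentence about all participants and does not say which arm it covers.
- **Analysis.** SAP 8.1: "All analyses will include the participant as the unit of analysis". The tables in SAP 8.3, 8.4.1, 8.4.2.1 and 8.4.3.1 repeat this unit. The only correlation they address is that of repeated measures within a participant, expected to be compound symmetric. There is no therapist effect, cluster-robust variance, design effect or therapist sensitivity analysis, and SAP 6 makes no allowance for clustering.
- **Number of therapists.** Not stated. The nearest figure is in Protocol 5.2, where 6 "study therapists and supervisors" are to be interviewed in Aim 3.

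**The concern.** This is a partially nested design: one arm is grouped by therapist and the other is not. If some therapists obtain better results than others, men who share a therapist have correlated outcomes, and the iCBT mean varies more than a model of independent participants implies. The interval for the arm contrast is then too narrow and the test rejects too often. The error favours declaring efficacy.

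The primary test has no other margin, since SAP 8.3 lists no control of type I error. SAP 6.3 bases interpretation of the secondary outcomes mainly on effect sizes, but the intervals around those effect sizes would be too narrow in the same way.

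**Working it through.** **Inputs from the documents.** 60 per arm, 1:1 (SAP 5.1); 20% attrition (SAP 6.2), so 60 × 0.8 = 48 analysed per arm; two-sided 5% (SAP 8.3); d = .40 (SAP 6.2).

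**Assumptions, not in the documents.** Therapists k = 3, 4 or 6 with equal caseloads; therapist ICC from 0 to .10; a continuous outcome compared by a two-sample test.

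**The plan's own figure.** SAP 6.2 claims at least 80% power for d = .40. A two-sample comparison with 48 per arm gives 50% (normal approximation; 49% by t-test), before any clustering. Averaging both follow-ups with baseline adjustment would give 79% at an assumed correlation of .5 and 84% at .6, but SAP 6.2 states no such basis. That is a separate matter; here 50% serves only as the reference for the power loss below.

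**Formulas.** With m = 48/k men per therapist:
- design effect in the iCBT arm only: DE = 1 + (m − 1) × ICC
- true SE / planned SE = √((1 + DE)/2)
- true level = 2 × [1 − Φ(1.96 / SE ratio)]

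**Examples at ICC .05.**
- k = 6: m = 8; DE = 1 + 7 × .05 = 1.35; SE ratio = √(2.35/2) = 1.084; 1.96/1.084 = 1.81; true level 7.1%.
- k = 3: m = 16; DE = 1 + 15 × .05 = 1.75; SE ratio = √(2.75/2) = 1.173; 1.96/1.173 = 1.67; true level 9.5%.

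**True level of the nominal 5% test, 48 per arm:**

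| ICC | 6 therapists | 4 therapists | 3 therapists |
|---|---|---|---|
| 0 | 5.0% | 5.0% | 5.0% |
| .01 | 5.4% | 5.6% | 5.9% |
| .02 | 5.8% | 6.3% | 6.8% |
| .05 | 7.1% | 8.3% | 9.5% |
| .10 | 9.2% | 11.5% | 13.8% |

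Simulating a t-test that ignores therapist gives, for 6 down to 3 therapists, about 5.3-5.8%, 6.0-6.6%, 7.1-9.3% and 9.3-13.9% at ICC .01, .02, .05 and .10. These agree with the formula to within about 0.2 percentage points.

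**Power when nesting is allowed for.** With k = 6 and ICC .05, SE = √(2.35/48) = 0.221, and power at d = .40 is Φ(.40/0.221 − 1.96) = 44%, against 50% without clustering. With small-sample degrees of freedom, simulation puts the fall at 49% to about 39%.

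**The case against.** **The ICC may be close to zero.** Content is standardised online text, video and exercises. Protocol 2.1 describes iCBT in general as asynchronous, with "counselors to then spend an average of only 10 minutes reviewing each module within 1-2 days". The primary endpoint falls about four months after the treatment window closes. This stands: a reader might infer that the standard error is too small as a matter of fact, but the documents give no ICC and nothing in them supports .05 or .10 in particular. Still, ten reviews of 10 minutes plus a 30-minute call is 10 × 10 + 30 = 130 minutes of individual therapist time before the check-in call. That is reason to estimate the ICC rather than take it as zero.

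**Six is not a ceiling.** A reader might infer at most six therapists. The figure combines therapists with supervisors and describes an interview sample. The sentence is also unreliable: its groups sum to 20 + 6 + 8 + 7 + 7 = 48, against a stated total of 55. There could be more than six. There could also be fewer, since Protocol 1.2 says one counselor can carry 200-300 cases.

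**Nesting alone does not inflate the error.** If iCBT has no effect through any therapist, or inference is confined to these therapists as fixed, the participant-level test keeps its level. Inflation requires therapist effects that differ and average zero over a wider population of therapists. That wider inference is the relevant one if the result is to support Aim 3, which concerns uptake in public and NGO settings where other counselors would deliver the programme.

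**The sentence in SAP 8.1 is not itself an error.** The participant is a proper unit under individual randomisation, and a model with a therapist random effect keeps that unit. The gap is that no model table specifies such an effect.

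**The adjusted model is imperfect.** With three therapists, simulation of a partially nested test with Satterthwaite degrees of freedom still gives 5.6-6.9%. This has been shown for a continuous outcome, not for a count GLMM fitted by maximum likelihood. This counts against making the adjusted model primary.

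**Conclusion.** The concern holds conditionally. The partial nesting is in the documents, and no planned analysis or sample-size step accounts for it. If the therapist ICC is above zero and the conclusion is meant to extend beyond these therapists, the primary and secondary contrasts are reported with too much precision, in favour of an effect.

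Under the stated assumptions the excess over 5% is under one point at ICC .01, about 2 to 4.5 points at .05, and about 4 to 9 points at .10. It depends on the ICC and on a therapist number that is probably small but unstated. It was calculated for a simple two-sample test, so for the planned count GLMM it shows direction and rough size only. The documents do not support saying that type I error certainly exceeds 5%, or that the participant-level model is wrong as the primary analysis.

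**What to change.** 1. Confirm whether the two-week check-in call in Protocol 6.1 also involves controls. If it does, treating each control as his own cluster may not be right.
2. Keep the participant-level model primary. In SAP 8.3 and 8.4, before arm comparisons are run, specify a partially nested sensitivity analysis: a therapist random effect on iCBT follow-up records only, each control as his own cluster, and small-sample degrees of freedom (Satterthwaite or Kenward-Roger) where the model allows them.
3. Report the number of therapists, the caseload of each and the estimated ICC.
4. Print the therapist-adjusted interval beside the primary one, and qualify any positive result that depends on ignoring therapist.

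The cost is SAP wording and one variable, therapist identity, which follows from an assignment the trial already makes. The second interval will be wider and, with few therapists, imprecisely estimated. If there is only one therapist, the variance component cannot be estimated; the report should then say so and limit the conclusion accordingly.
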